3.4.7.2 Prior and Concomitant Treatments

Prior treatments, defined as those taken within 2 wk before Screening, should be recorded in the eCRF as prior medications. Concomitant treatments, defined as treatments taken after the first dose of study drug, should be recorded in the eCRF as concomitant medications. Concomitant medications will be coded using the latest version of the World Health Organization Drug Dictionary.

Use of medications with known vasoconstrictive properties (eg, decongestants [Afrin[®], Sudafed[®]]) currently or within 2 h prior to Screening are not permitted.

Any medication or therapy that is taken by or administered to the subject during the course of the study must be recorded in the eCRF. The entry must include the dose, regimen, route, indication, and dates of use. The following medications are prohibited until the end of the treatment period on Day 1 (ie, 60 min post dose):

- Medications with known vasoconstrictive properties (eg, decongestants [Afrin[®], Sudafed[®]])
- Oral analgesics

3.5 Assessments

Unless otherwise indicated, all assessments will be performed by the investigator or designated study personnel.

3.5.1 Schedule of Assessments

The procedures to be performed throughout the study are outlined in the Schedule of Assessments (Table 3.2). A detailed description of each assessment may be found in Section 3.5.2.

Table 3.2: Schedule of Assessments

Study Period	Screening/ Baseline	Treatment				Safety Follow-up Telephone Call/ Study Exit	
Study Day	1				1		7
Study Minute	N/A	0	10	20	30	60/Early Termination	N/A
Informed Consent	Х						
Demographics	Х						
Inclusion/Exclusion Criteria	Х						
Medical History	Х						
Physical Examination ^a	Х						
ENT Examination ^{b,c}	Х					Х	
Urine Pregnancy Test ^d	Х						
Randomisation ^e	Х						
Vital Signs and Body Weight ^f	Х					Х	
NRS-11 ^g	X ^h		X	Χ	Χ	Х	
VAS ^g	X ⁱ		X	Χ	Χ	Х	
Otoscopy ^{c,j}	Х					Х	
PGIC			X	Χ	Χ	Х	
CGI-I ^k						Х	
AOM Symptoms ¹	Х					Х	
BI ^m						Х	
Device Experience Questionnaire- Subject						Х	
Device Experience Questionnaire-Study Staff Administering the Treatment ⁿ						X	
Study Drug Administration ^o		Χ					
Prior and Concomitant Medications	X ^p	XX		Х			
AEs		XX		Х			

Examination will include general appearance, skin, neck (including thyroid), eyes, heart, lungs, abdomen, lymph nodes, а extremities, and nervous system.

b Otoscopy of the ear, nose, and oropharynx.

с

To be performed by a physician investigator. For all female subjects of childbearing potential. Results must be available prior to randomisation. d

- ^e Subjects will be randomly assigned to OP0201 20 mg or placebo in a 1:1 ratio (OP0201:placebo) following screening procedures, but prior to baseline and treatment procedures.
- ^f Oral temperature, respiratory rate, pulse, and BP measured after at least 3 min of rest in the supine position will be performed at Baseline and at 60 min post dose. Body weight will be measured at Baseline only.
- ^g Both ears will be evaluated regardless if AOM is bilateral or unilateral.
- ^h Administered to assess pain in both ears during the screening procedures. This score will also serve as the baseline measure for affected ear(s).
- ⁱ To be administered after randomisation.
- ^j Appearance of the TM will be rated for contour (normal, retracted, full, bulging, perforated), color (normal, partly red, completely red), fluid behind the TM (no/yes; if yes-yellow, translucent, red, blue, or black), and translucency (translucent, semi-opaque, and opaque). Both ears will be evaluated regardless if AOM is bilateral or unilateral.
- ^k To be completed by the physician investigator who evaluated the subject at baseline and post dose.
- ¹ AOM symptoms to be evaluated include tinnitus, dizziness, vertigo, and feeling of fullness or muffled hearing in the ear.
- ^m To be administered to the subject and physician investigator separately after completion of all other assessments.
- ⁿ To be obtained only once by each qualified staff member who administers the study treatment to subjects in this study.
- ^o 4 sprays of intranasal OP0201 20 mg or placebo will be delivered to each nostril for a total of 8 sprays.

^p Prior medications will only be recorded at Screening.

Abbreviations: AE = adverse event; AOM = acute otitis media; BI = Blinding Index; BP = blood pressure; CGI-I = Clinical Global Impressions Scale: Global Improvement; ENT = ear, nose, and throat; min = minute(s); N/A = not applicable; NRS-11 = Numeric Rating Scale; PGIC = Patient Global Impression of Change; TM = tympanic membrane; VAS = Visual Analog Scale

3.5.2 Study Procedures

3.5.2.1 Screening/Baseline Procedures (Day 1)

The assessments during the screening/baseline phase will determine the subjects' eligibility for the study and also their ability to comply with protocol requirements by completing all screening/baseline assessments.

The following procedures will be performed and recorded during the screening/baseline period:

- Written informed consent
- Demographics
- Inclusion and Exclusion Criteria
- Medical history
- Physical examination
- ENT examination (physician investigator to perform otoscopy of the ear, nose, and oropharynx)
- Urine pregnancy test (for all female subjects of childbearing potential; results must be available prior to randomisation)
- Vital signs (oral temperature, respiratory rate, pulse, and blood pressure measured after at least 3 min of rest in the supine position) and body weight
- Randomisation
- NRS-11 (score will be used to assess pain in both ears during Screening and as the baseline measure for affected ear(s); both ears will be evaluated regardless if AOM is bilateral or unilateral)
- VAS (to be administered after randomisation; both ears will be evaluated regardless if AOM is bilateral or unilateral)
- Otoscopy (physician investigator to evaluate contour, color, fluid, and translucency)
- AOM symptoms (tinnitus, dizziness, vertigo, and feeling of fullness or muffled hearing in the ear)
- Prior and concomitant medications

3.5.2.2 Treatment Procedures (Day 1)

After completion of all screening/baseline procedures, subjects will receive a single intranasal dose (4 sprays per nostril for a total of 8 sprays) of OP0201 20 mg or placebo. Reported AEs will be recorded.

At 10, 20, and 30 min post dose, the following procedures will be performed:

- NRS-11 (both ears will be evaluated regardless if AOM is bilateral or unilateral)
- VAS (both ears will be evaluated regardless if AOM is bilateral or unilateral)

- PGIC
- AEs and concomitant medications

At 60 min post dose, the following procedures will be performed:

- ENT examination (physician investigator to perform otoscopy of the ear, nose, and oropharynx)
- Vital signs (oral temperature, respiratory rate, pulse, and blood pressure measured after at least 3 min of rest in the supine position)
- NRS-11 (both ears will be evaluated regardless if AOM is bilateral or unilateral)
- VAS (both ears will be evaluated regardless if AOM is bilateral or unilateral)
- Otoscopy (physician investigator to evaluate contour, color, fluid, and translucency)
- PGIC
- CGI-I (obtained from the physician investigator who evaluated the subject at baseline and post dose)
- AOM symptoms (tinnitus, dizziness, vertigo, and feeling of fullness or muffled hearing in the ear)
- AEs and concomitant medications
- BI (to be administered separately to the subject and physician investigator after completion of all other assessments)
- Device Experience Questionnaire-Subject
- Device Experience Questionnaire-Study Staff Administering Treatment

3.5.2.3 Safety Follow-up Telephone Call/Study Exit

• AEs and concomitant medications

3.5.3 Early Termination Procedures

The following assessments will be administered to subjects who terminate prematurely from the study:

- ENT examination (physician investigator to perform otoscopy of the ear, nose, and oropharynx)
- Vital signs (oral temperature, respiratory rate, pulse, and blood pressure measured after at least 3 min of rest in the supine position)
- NRS-11 (both ears will be evaluated regardless if AOM is bilateral or unilateral)
- VAS (both ears will be evaluated regardless if AOM is bilateral or unilateral)
- Otoscopy (physician investigator to evaluate contour, color, fluid, and translucency)
- PGIC

- CGI-I (obtained from the physician investigator who evaluated the subject at baseline and post dose)
- AOM symptoms (tinnitus, dizziness, vertigo, and feeling of fullness or muffled hearing in the ear)
- AEs and concomitant medications
- BI (to be administered separately to the subject and physician investigator after completion of all other assessments)
- Device Experience Questionnaire-Subject

Clinical Global Impressions Scale: Global Improvement (CGI-I): The CGI-I assesses the physician investigator's global impression of global change from Baseline in symptoms since the administration of study drug. The CGI-I instructions are as follows: "How has the subject's symptoms been since they received the study treatment?" Scores range from 1 to 7, with 1 = very much improved, 2 = much improved, 3 = minimally improved, 4 = no change, 5 = minimally

Confidential

worse, 6 = much worse, and 7 = very much worse. The CGI-I will be evaluated at 60 min post dose.

AOM Symptoms: The following AOM symptoms will be evaluated predose and at 60 min post dose: (1) tinnitus, (2) dizziness, (3) vertigo, and (4) feeling of fullness or muffled hearing in the ear. The investigator will record for each subject whether the symptom is present or absent.

3.5.5 Safety Assessments

Ear, Nose, and Throat Examination: Examination of the ear, nose, and oropharynx will be performed using otoscopy at Screening and at 60 min post dose.

Otoscopy: Otoscopy assessments will be performed by the physician investigator to assess the appearance of the TM in the left and right ear. Measurements will be taken at Baseline and at 60 min post dose. The TM will be rated for the following variables:

- Contour: normal, retracted, full, bulging, or perforated
- Color: normal, partly red, or completely red
- Fluid behind the TM: no/yes; if yes-yellow, translucent, red, blue, or black
- Translucency: translucent, semi-opaque, or opaque

Details of how each variable is to be assessed and categorised are provided in Appendix 8.2.

Vital Signs: Vital signs will be measured at Baseline and at 60 min post dose or Early Termination. Vital signs will include oral temperature (C), respiratory rate (breaths per minute), pulse (beats per minute [bpm]), and systolic and diastolic blood pressure (BP) recorded after at least 3 min of rest in the supine position. Body weight (kg) will also be collected with the vital signs measurements at Baseline only. Repeat measurements may be obtained in the event the initial measurements taken at Baseline are out of range.

Adverse Events: All AEs occurring after the administration of study treatment until the follow-up safety call or early termination will be recorded.

See Section 4, for additional information.

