Any study staff who administer treatment to subjects will also complete the Device Experience Questionnaire. Any study staff who administered treatment only needs to complete the questionnaire one time for the study, not for each subject treated.

Subjects will receive a follow-up safety call 1 wk after treatment, and reported AEs and concomitant medications will be recorded.

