3.3.3 Removal of Subjects from Therapy or Assessment

A subject will be considered to have completed the study when he or she completes the follow-up safety call on Day 7. If a subject is discontinued at any time after randomisation into the study, but before 60 min post dose, the investigator will make every effort to follow the

subject and complete the assessments at 60 min post dose/early termination assessments as shown in Section 3.5.1. Subjects who discontinue the study prematurely will be replaced.

A termination electronic case report form (eCRF) page should be completed for every subject who receives study drug, whether or not the subject completes the study. The reason for any early discontinuation should be indicated on this form. The primary reason for a subject discontinuing early should be selected from the following standard categories of early termination:

- *Adverse Event (Adverse Reaction)*: Clinical events occurred that, in the medical judgment of the investigator for the best interest of the subject, are grounds for discontinuation. This includes serious and nonserious AEs regardless of relation to the study drug.
- *Death:* The subject died.
- *Withdrawal of Consent*: The subject desired to withdraw from further participation in the study in the absence of an investigator-determined medical need to withdraw. If the subject gave a reason for withdrawing, it should be recorded in the eCRF.
- *Protocol Violation*: The subject's findings or conduct failed to meet the protocol entry criteria or failed to adhere to the protocol requirements (eg, drug noncompliance, failure to complete all assessments). The violation necessitated early discontinuation from the study.
- *Lost to Follow-Up*: The subject did not complete the follow-up safety call and study personnel were unable to contact the subject.
- *Other*: The subject was discontinued for a reason other than those listed above, such as theft or termination of study by sponsor.

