4.2 Study Endpoints

4.2.1 Primary Endpoints

Primary endpoints are related to safety:

- Incidence, seriousness, severity, and relatedness to study treatment of adverse events (AEs) recorded over 60 minutes post dose and at Day 7
- Change from Baseline in vital signs (oral temperature, respiratory rate, pulse, blood pressure) at 60 minutes post dose
- Change from Baseline in ear, nose, and throat (ENT) examination (otoscopy of the ear, nose, and oropharynx) findings at 60 minutes post dose
- Change from Baseline in the appearance of the tympanic membrane (TM) (contour, color, fluid, translucency) as measured by otoscopy at 60 minutes post dose

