8.6 Study Period and Time Point Definitions

Screening: Day 1 up to dosing.

Baseline Observation: for a given parameter for a given randomized Study Participant, the last observed value before the first dose of study treatment or planned first dose of study treatment if not dosed.

Study Day 1: for a given randomized Study Participant, the day of actual first dose of study treatment or planned first dose of study treatment if not dosed.

Study Day:

- Study day = date of assessment date of dosing + 1, for assessments on or after first dose
- Study day = date of assessment date of dosing, for assessments before first dose

Study Time: time of assessment – time of first dose

Duration:

- Duration in days = end date start date + 1
- Duration in minutes = end time start time

(Nominal Visit) Analysis Time Point: analysis based on data collected at the (nominal visit) time point, where nominal visits are as shown below in Section 8.7.

End of Study (EOS), Study Participant-Level: the date of completion of the last planned study visit or date of discontinuation for any reason.

EOS, Study-Level: the date when all randomized Study Participants have reached Study Participant-Level EOS.

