11. SAFETY PARAMETERS

Safety parameters will be listed for the Randomized Population and summarized for the Safety Population unless otherwise noted.

11.1 **AEs**

AEs reported from time of first dose through EOS will be coded according to MedDRA® version 21.1 or later. Each reported AE will be mapped to a PT and SOC. Aside from parameters collected on the eCRF, listings will include date and time of study treatment dosing, MedDRA PT and SOC, Study Day, whether or not the AE is ongoing, AE duration, and whether or not the AE resulted in study discontinuation. For AEs that are ongoing, AE end date will be imputed with subject-level EOS date for the duration calculation.

A treatment-emergent AE (TEAE) will be defined as an AE that began or worsened during or after study treatment dosing on Day 1 and no later than on Day 2. AEs with insufficient date or time information to determine whether or not they were treatment-emergent will be considered treatment-emergent. AEs that began or worsened in severity from Day 3 through EOS will be defined as non-treatment-emergent. AEs that began or worsened in severity before first dose will be recorded as medical history.

All TEAEs will be listed. In addition, separate listings will be done for:

- Treatment-emergent SAEs (TESAEs), to include seriousness criteria
- TEAEs that resulted in study treatment interruption or dose reduction

Confidential Page 16 of 33

- TEAEs that results in discontinuation from the study or study treatment (excluding deaths)
- TEAEs that resulted in death
- Non-treatment-emergent AEs

Listings will be done for the Safety Population.

Incidence of all TEAEs will be summarized by SOC and PTs within SOCs, sorted alphabetically by SOC and PT within SOC unless otherwise noted. In addition, separate summaries will be done for:

- TEAEs assessed as related to study treatment
- TEAEs by maximum severity, with both SOCs and PTs within SOCs sorted by descending incidence among all Study Participants combined
- TESAEs
- TESAEs assessed as related to study treatment

In summaries by relationship to study treatment and maximum severity, missing relationship will be considered related and missing severity will be considered severe. Only the most related TEAE per subject for a given PT will be counted in summaries by relationship; similarly, only the most severe TEAE will be counted in summaries by severity.

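### Collection of new AEs ends at early termination, although the primary AE endpoint reaches Day 7 and dosed leavers stay in the denominator

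*Protocol*

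**What the plan says.** **Planned observation.** Protocol 3.1 says: "Subjects will receive a follow-up safety call 1 wk after treatment, and reported AEs and concomitant medications will be recorded". SAP 4.2.1 defines the first primary endpoint as: "Incidence, seriousness, severity, and relatedness to study treatment of adverse events (AEs) recorded over 60 minutes post dose and at Day 7".

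**When collection stops.** Protocol 3.5.5 says: "All AEs occurring after the administration of study treatment until the follow-up safety call or early termination will be recorded". The SAP agrees. In 11.1, "AEs reported from time of first dose through EOS will be coded according to MedDRA", and 8.6 defines participant-level EOS as "the date of completion of the last planned study visit or date of discontinuation for any reason". For an early leaver, EOS is therefore the day of leaving.

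**What happens at exit.** Protocol 3.5.3 introduces its list with "The following assessments will be administered to subjects who terminate prematurely from the study". The list has one check of AEs and concomitant medications and no Day 7 call. For a subject discontinued after randomisation but before 60 minutes, 3.3.3 says "the investigator will make every effort to follow the" subject, with the stated aim of completing the 60-minute/early termination assessments. The same section adds: "Subjects who discontinue the study prematurely will be replaced".

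**Who is counted.** The Safety Population is everyone dosed (Protocol 5.2.2, SAP 7). Protocol 5.2.7.2 reports TEAE incidence as a number and percentage of subjects. SAP 8.5 imputes nothing in summaries.

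**The concern.** Safety is the only primary objective, and Protocol 1.1.2 says that OP0201 has not been studied in humans before. All eight sprays are given at minute 0, so a subject who leaves is still exposed but no longer observed. A new AE that evening or later in the week falls outside both the protocol's recording rule and the SAP's coding rule, while the subject still counts in the denominator. With about 12 subjects per arm, one missed event is visible in the percentage. The planned tables do not state how many dosed subjects lacked Day 7 contact.

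**Working it through.** **1. Does another clause close the gap?**

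- Protocol 4 has AEs followed until resolved or stable. This covers AEs that have already occurred, not new ones.
- Protocol 4.2.1 and 4.2.2 have related or possibly related AEs and SAEs reported when detected after the follow-up safety call. Neither mentions subjects who left before that call.
- Protocol 3.3.3 asks for effort to follow subjects who leave before 60 minutes, but only as far as the 60-minute/early termination assessments.

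None gives an explicit route for a new event on, say, Day 3 in a dosed subject who left on Day 1.

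**2. Which window is lost?** SAP 11.1 counts an AE as treatment-emergent only if it began or worsened no later than Day 2. Events from Day 3 to EOS go to Table 14.3.1.4.

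| Output | Window lost to an early leaver |
|---|---|
| TEAE tables | Exit to end of Day 2; nothing if exit is on Day 3 or later |
| Non-treatment-emergent table | Day 3 (or exit, if later) to Day 7 |
| Day 7 part of the primary endpoint | Exit to Day 7 |

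**3. Which subjects matter?** A subject who leaves because of an AE is already counted in any-AE incidence. For that subject only a later new preferred term, worsening or seriousness can be missed. Any-AE incidence loses a case only when a leaver was event-free at exit and had an event afterwards.

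**4. Size.** The plan's only relevant figure is its sample size, 2 × 12 = 24, which agrees. It gives no AE rate or dropout rate, so the values of r, f, k and d below are assumptions.

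*Ceiling per subject:* 1/12 = 8.3 points. If the replacement falls in the same arm, 1/13 = 7.7 points.

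*Expected understatement:* let n = 12, k = leavers in the arm, r = true incidence over the window, f = share of that risk falling after exit. Crude incidence is r × [(n − k) + k(1 − f)]/n, so the understatement is r × k × f/n.

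| k | Low: r = 10%, f = 0.25 | High: r = 50%, f = 1 |
|---|---|---|
| 1 | 0.10 × 1 × 0.25/12 = 0.2 points | 0.50 × 1 × 1/12 = 4.2 points |
| 2 | 0.10 × 2 × 0.25/12 = 0.4 points | 0.50 × 2 × 1/12 = 8.3 points |

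*Bounds for an arm with one AE case and one other subject who left event-free:* crude 1/12 = 8.3%; leaver excluded 1/11 = 9.1%; leaver counted as an event 2/12 = 16.7%.

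*Chance of at least one leaver among 24:* 1 − (1 − d)^24 gives 38%, 71% and 92% for d = 2%, 5% and 10%.

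**The case against.** The strongest defence is that protocol and SAP agree, so this is a design choice rather than a contradiction, and that it does little harm. Dosing is single and given by staff, the main tables close at Day 2, an AE that prompts withdrawal is counted and followed, and 3.3.3 asks for the 60-minute assessments. Disposition is also open to inspection: SAP 9.1 summarises discontinuations with reasons and lists dosing and EOS dates. All of this stands and limits the size of the problem. It does not supply the missing observation.

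One could also say that 3.1 already promises every subject the call. But then the early termination limit in 3.5.5 would have no function, and 3.5.3 omits the call. Sites could read the text either way.

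A Day 7 call also cannot recover everyone. Subjects lost to follow-up are defined in 3.3.3 by not completing that call, and those who withdraw consent to contact cannot be phoned.

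A reader might infer more than the documents support:

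- **That AE-driven withdrawals bias any-AE incidence downward.** They do not, because those subjects are already cases.
- **That a subject leaving at minute 20 gives only 20/10,080 = 0.2% of the planned observation.** That uses the full week, which is the wrong denominator for the TEAE tables, and ignores the effort to complete the 60-minute assessments.
- **That incidence could be 2/12 = 16.7 points too low.** This needs two leavers in one arm, both event-free at exit and both with a later unrecorded AE, and no replacement in that arm.
- **That the SAP's 10% figure bounds early termination.** SAP 13.1.4 concerns missing observations in the exploratory analyses.
- **That the plan declares leavers fully observed.** This is only an implication of the crude percentage.

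**Conclusion.** The point holds in a limited form. Both documents end collection of new AEs at early termination, no later contact is planned, and dosed leavers stay in a crude denominator for an endpoint that reaches Day 7. The likely effect is small. The 8.3 points per subject is a ceiling, and 0.2 to 4.2 points for one leaver rests on an assumed incidence of 10% to 50% with 25% to 100% of the risk falling after exit. The bias in any-AE incidence comes only from leavers who were event-free at exit. The change is worth making because it concerns the primary endpoint and costs almost nothing, not because the planned result would be seriously distorted.

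**What to change.** - **Protocol 3.5.5:** record AEs up to the Day 7 safety call for every subject who received any study drug, including those who terminate early, unless consent to contact is withdrawn.
- **Protocol 3.5.3:** add the Day 7 call to the early termination procedures.
- **SAP 8.6 and 11.1:** for AEs and concomitant medications, end the period at the Day 7 call or last contact rather than at discontinuation.
- **SAP tables:** report by arm the number of dosed subjects without Day 7 contact, for example as a footnote to the AE summary.

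The cost is one call per reachable early leaver and a few sentences of text. Observed AE incidence may come out slightly higher. If enrolment is already over, as the past tense in SAP 9.2 suggests, the SAP changes can still be made; the by-arm count is then the most useful of them.
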